8.4 Study treatment administration

All patients enrolled, randomized in Arm A or B, will receive successive 28-day courses of subcutaneous low-dose cytarabine 40 mg daily (or 20 mg twice daily) for 10 days per course (from day 1-D1 to day 10-D10), each course occurring every 28 days +/- 3 days, for a duration up to 24 months. SPC for Cytarabine Hospira and Pfizer are attached in Appendix 1 as example. Please refer to country-specific approved Cytarabine SPC for country-specific information.

Following the implementation of Amendment 4, patients randomized in arm B treatment will receive subcutaneous low-dose cytarabine, as described above, and GRASPA 100 IU/kg, given as an intravenous infusion at **Day 11** of each 28-day course.

Required documents such as **Investigator's prescription of GRASPA and Patient's pretransfusional status** (refer to section 9.6) should be sent at ERYTECH Pharma 2 days before the schedule day of GRASPA administration, i.e. Day 9.

In the event the patient cannot receive GRASPA treatment at the planned date (i.e. manufacturing failure) or if GRASPA treatment received on site is not suitable for administration (e.g. transport or cold chain impairment, rupture of bag...), investigator and ERYTECH Pharma will discuss the best treatment approach for the patient:

- Restart manufacture for a new bag of GRASPA (delay GRASPA administration with max one week), if acceptable for the patient.
- Switch the patient to appropriate alternative treatment, at investigator's decision.
 - If the switch occurred before the first GRASPA administration, then the patient will be replaced, as defined in section 7.6.
 - If the switch occurred after at least one administration of GRASPA, treatment for next blocks afterwards will be at investigator's decision (GRASPA will not be resumed if delayed more than 2 weeks; refer to section 8.5.4 "Dosage modifications of GRASPA" and 8.11 "end of study treatment").

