 - Collection and Review of previous patient diary completed
- End of study treatment
 - Disease evaluation (AML) (see section 8.6)
 - Clinical assessment: vital signs, performance status (ECOG score), physical examination findings

- Patient quality of life: survey EORTC QLQ-C30, transfusion needs, hospitalizations from any cause (except scheduled protocol visit)
- Primary reason for treatment termination
- Subsequent AML treatment if any
- Collection and Review of previous patient diary completed
- Review and assessment of any adverse event (refer to section 11 for details)
- Follow-up visit after end of study treatment (every 3 months +/- 2 weeks after End of Treatment visit ex. M3, M6, M12...)
 - Disease evaluation, in the case relapse/recurrent status had not already occurred and the patient was discontinued from the treatment for other reason
 - Patient quality of life: survey, transfusion needs, hospitalizations from any cause (except scheduled protocol visit)
 - Clinical assessment: Survival status
 - Review and assessment of any adverse event (refer to section 11 for details)
 - At minimum, a phone call will be performed 4 months (+/- 1 week) after end of treatment, for safety assessments

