8.11 End of study treatment

Patients will stop study treatment in following situations:

- Disease relapse or presence of a resistant disease, unless the investigator considers that the patient has a clinical benefit from continuing the treatment. In this case, the investigator should continue to perform the same study visits as long as considered clinical beneficial.
- Occurrence of GRASPA-related toxicity, such as:
 - Grade 3 or 4 pancreatic toxicity
 - o Grade 3 or 4 hepatic toxicity, allergic reaction, or coagulation event
 - o other non-hematologic Grade 4 toxicity

Patient assessment should continue as planned until evidence of relapse or presence of a resistant disease, in which case, patient will be followed up for survival.

- Patient unwilling to continue
- No evidence of study treatment benefit at investigator's decision

9. Investigational product: GRASPA

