3.4. Study Procedures

The schedule of assessments, as outlined in the study protocol, is provided in Table 1.

Table 1: Schedule of Assessments

Day	D – 28 max.	TREATMENT COURSE – 28 days cycle (+/- 3 days)													
		1	2	3	4	5	6	7	8	9	10	11	13	18	23
Visit	Inclusion	1/2/3 ...													
Consent	X														
Demographics	X														
Inclusion/exclusion criteria	X														
Medical history	X														
AML history/ assessment (a)	X														X*
Clinical assessment (b)		X													
Quality of life survey		X													
Randomization	X														
Low-dose cytarabine		X	X	X	X	X	X	X	X	X	X				
GRASPA										P		X			
IAST (c)										X					
PK- PD (only for GRASPA receiving patients) (d)											X	X	X		X
Immunogenicity (only before GRASPA administration)											X				
Biology (e)	X	X (f)			X			X			X	X	X	X	X
Patient diary distribution and/or review		X													

(a) Bone marrow aspiration and extramedullary assessment may take place in the 4 weeks prior to randomization, for baseline status; samples for biomarkers assessments should be sent within max. 2 days after collection;

(b) including occurrence of AE/SAE; concomitant treatment;
(c) Irregular Antibodies Screening Test only for patients receiving GRASPA;
(d) See PK-PD assessments table 5
(e) hematology (CBC) ; biochemistry ; coagulation parameters; serology tests only at inclusion; pregnancy test at inclusion and end of treatment, if applicable
(f) for the first course = if biochemistry/hematology tests are available within 7 days, it is not necessary to repeat them; for coagulation tests – results should not be older than 3 days; for subsequent courses = to be performed within max. 3 days before next treatment course start;
P : prescription of GRASPA;

*: before the next treatment course

Table 2: Calendar of Study PK/PD Assessments

Table 3: Calendar of Study Assessments – Follow-Up

Visit	End of treatment	every 3 Months until M24 (M3, ...)* +/- 2 weeks
AML assessment	X	X
Clinical assessment, including Adverse events review and assessment and Concomitant medications	X	X
Quality of life survey	X	X
Subsequent AML therapy	X	X
Patient diary return and review	X	

*: a phone call, at minimum, will be performed at 4 months (+/- 1 week) after end of study treatment, for safety assessment
Patient will have to attend visit every 28 days (+/- 3 days), at the start of each cycle, for a duration up to 24 months. Assessments required are provided in Tables 1 and 2.

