5.6. Efficacy Evaluation

All efficacy analyses will be performed on the ITT population. Analyses on the primary efficacy endpoint will be repeated on the PP population.

Primary Endpoint Definition and Analysis

The primary endpoint, OS, will be defined as the time elapsed between date of randomization and date of death (or censoring) from any cause. Any patient not known to have died at the time of analysis will be censored based on the last recorded date on which the patient was known to be alive.

The primary objective of the trial is to estimate whether GRASPA plus LDAC is more promising than LDAC alone with respect to OS in subjects from 65 to 85 years old with newly diagnosed AML unfit for intensive chemotherapy.

Overall survival will be summarized by treatment group for the ITT population. Summaries will include the number of patients who died during the study, the number of patients who didn't die during the study (censored) with the date of censoring equal to the date that the patient was last known to be alive. Median time-to-event will be estimated from a Kaplan-Meier analysis, with associated survival curves produced. The p-value for this analysis will be provided from the stratified log-rank test, with stratification variable of type of ECOG performance status (0 or 1 versus 2) and will compare the overall survival curves between the two treatment groups. In addition, the hazard ratio and its associated 95% CI will be estimated from a stratified Cox proportional hazards model using the same strata as the Kaplan-Meier analysis (ECOG status) and censoring rules. Forest plots for the OS hazard ratios for the subgroups detailed in Section 4.2.6 will also be produced.

OS event rates at Months 12 and 24 will be summarized by treatment group for the ITT population. Summaries will include the event rate for each treatment group from the Kaplan-Meier analysis, using the estimated proportions at Month 12 and 24. A 95% CI for the difference in event rates between the treatment groups will also be provided.

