5.6.2. Secondary Endpoint Definitions and Analyses

Secondary endpoints will be assessed on both the ITT and PP populations.

5.6.2.1. Complete Remission (CR), Complete Remission with Incomplete Recovery (neutrophil or platelet recovery, CRi, CRp), Partial Remission (PR)

Definitions for CR, CRi, and PR can be found in Table 4 below. This information will be collected in the section “AML-disease evaluation.” Responses are entered by the site in accordance with various criteria. Exploratory analyses may include imputed responses (not site defined) based on the data available per the criteria in Table 4 for the derivation of response.

Table 4: Definitions of CR, CRi, PR, Relapse

Category	Definition according to protocol V4 to V6	Definition according to protocol V7
Morphologic leukemia-free state	Bone marrow blasts < 5% No extramedullary disease	
Complete remission (CR)	Morphologic CR Bone marrow blasts < 5%; absence of blasts with Auer rods; absence of extramedullary disease; absolute neutrophil count $> 1.0 \times 10^9/L$ (1000/ μ L); platelet count $> 100 \times 10^9/L$ (100 000/ μ L); patient independent of transfusions Cytogenetic CR Cytogenetic normal (in those with previously abnormal cytogenetics) Molecular CR Molecular studies negative	
CR with incomplete recovery (CRi)	All CR criteria except for residual neutropenia ($< 1.0 \times 10^9/L$ [1000/ μ L]) OR thrombocytopenia ($< 100 \times 10^9/L$ [100 000/ μ L]). patient independent of transfusions	
Partial remission (PR)	All hematologic criteria of CR; decrease of bone marrow blast percentage to 5% to 25% And normalization of blood counts	
Relapse following CR	Bone marrow blasts $\geq 5%$; OR reappearance of blasts in the blood OR Development of extramedullary disease	

Percentages of patients with CR, CR or Cri, and PR will be calculated and presented by treatment group. All other subjects will be considered non-responders for determining the denominator. This objective response rate data (i.e. CR, CRi or PR) will be analyzed based on a logistic regression model with both treatment and PS included in the model. The treatment effect will be summarized with an adjusted Odds Ratio (OR) and 95% confidence interval. Percentage of patients with objective response will be calculated and associated exact 95% CIs will be presented by treatment group.

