5.6.2.2. Progression-Free Survival (PFS)

PFS was originally defined as death due to progression in the protocol. However, to be consistent with regulatory guidance, which considers death from any cause in its definition, this endpoint was modified to be time elapsed between randomization and disease progression or death from any cause. Patients not known to have any of these events will be censored on the date they were last known to be event-free.

Progressive disease (PD) will be defined according to the section “AML-DISEASE EVALUATION” in the e-CRF as any of the following

- At least a 25% increase of BMBC compared with baseline (defined in the section “AML history / BM evaluation at baseline”, Bone Marrow Aspirate - Analyte - Blast)
- At least a 50% increase of PBBC compared with baseline
- Presence of extramedullary disease

Potential PD events presented by the patients will be reviewed and approved before database lock.

The methods for the analysis of PFS will be the same as those for OS. Specifically, PFS will be analyzed at the time of final analysis using a stratified log-rank test (stratified by PS) and displayed using Kaplan-Meier curves. Furthermore, a Cox model will also be used to test the effect of treatment and will include terms for prognostic factors (PS, age and karyotypic group).

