5.8.4. Concomitant Medications

Concomitant medications will be coded using the WHO Drug dictionary. Results will be tabulated by Anatomic Therapeutic Class (ATC) and preferred term.

The use of concomitant medications will be included in by-subject data listing.

Previous medications are defined as medications reported with a stop date prior or equal to the date of inclusion. In case of partial/missing stop date the following rules will be applied:

- If only the day is missing: month and year of stop date will be used to determine whether the medication is prior or concomitant
- If day and month are missing: the year of stop date will be used to determine whether the medication is prior or concomitant
- If the stop date is missing the medication will be considered as prior and concomitant

All other medications reported will be considered as concomitant. Previous and concomitant medications will be described in each treatment group according to their therapeutic class (ATC) and preferred term (PT) (WHO Drug Dictionary, version of March 2013).

The previous and concomitant medications will be summarized by treatment group in the ITT population.:

- The number and percentage of patients presenting at least one previous medication will be described in each treatment group.
 - The previous medication will then be presented per ATC and PT in a frequency table in each treatment group.
- The number and percentage of patients presenting at least one concomitant medication will be described in each treatment group.
 - The concomitant medication will then be presented per ATC and PT in a frequency table, in each treatment group.

The medications given for type II diabetes will be presented.

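### The SAP sets no stop for counting responses when later AML therapy starts, so a remission reached on another drug is credited to the randomised arm

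*SAP*

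**What the plan says.** **Response.** SAP 5.6 states "All efficacy analyses will be performed on the ITT population". Under SAP 5.6.2.1, sites enter CR, CRi and PR, and "All other subjects will be considered non-responders for determining the denominator". That sentence settles who is a non-responder. Nothing nearby limits when a response must occur or which treatment the patient must be on.

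**PFS and RFS.** SAP 5.6.2.2 states "Patients not known to have any of these events will be censored on the date they were last known to be event-free", and SAP 5.6.2.3 has the same rule for RFS. New therapy is neither an event nor a censoring point.

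**Collection.** Protocol Table 6 and SAP Table 3 both carry a row "Subsequent AML therapy", marked at end of treatment and at the 3-monthly visits to month 24. The text of protocol 8.10 lists "Subsequent AML treatment if any" under the end-of-treatment visit only.

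**Routes off treatment.** Protocol 8.11 lets either arm stop for "No evidence of study treatment benefit at investigator's decision" or because the patient is unwilling to continue. It also lists GRASPA-related toxicity. When a GRASPA bag cannot be made or used, one option in protocol 8.4 is: "Switch the patient to appropriate alternative treatment, at investigator's decision".

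**After leaving treatment.** Protocol 8.10 continues disease evaluation at follow-up visits for patients who stopped for another reason and have not relapsed. Protocol 8.11 continues assessment after a toxicity stop until relapse or resistant disease.

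**The concern.** A patient can stop study treatment with stable disease, start another AML drug, and be in CR at the next 3-monthly evaluation. Under SAP 5.6.2.1 that CR is a response for the randomised arm, although the study regimen did not produce it.

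This matters because SAP 1 judges GRASPA on the totality of evidence across endpoints, and response is one of them. The trial is open label, so the decision to stop and the choice of next drug are made with the arm known. The planned outputs named in SAP 8.1 include no by-arm summary of later therapy to set beside response, PFS or the OS hazard ratio.

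**Working it through.** The plan gives no figure for later therapy, so there is none to reproduce. The check is of the rules first, then of what one patient or a plausible group of patients would do.

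**1. The rules applied in order.** Take an arm B patient switched to alternative treatment under protocol 8.4.
- The ITT definition (SAP 4.1) keeps the patient in arm B whatever was received. Protocol 8.4 calls for replacing patients switched before the first GRASPA dose, whereas SAP 5.2.7 says withdrawn subjects were not to be replaced. Neither removes the patient from arm B under ITT.
- If there is no relapse or resistant disease, evaluation goes on (protocol 8.10).
- A CR entered by the site then counts (SAP 5.6.2.1).

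The same sequence applies to an arm A patient stopped for lack of benefit. The SAP does use cut-offs elsewhere: transfusions and hospitalisations after PD are not counted (SAP 5.6.2.4, 5.6.2.6). There is no equivalent for new therapy.

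**2. Size per patient.** Planned arms are 82 (B) and 41 (A).
- One later-drug responder in arm B: 1/82 = 1.2 percentage points.
- One in arm A: 1/41 = 2.4 percentage points.

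**3. Illustration for response (assumed values).** Assume no true effect and a response rate of 18% in both arms. That is the low-dose cytarabine CR rate cited in protocol 3.1. Let an extra fraction f of arm B non-responders take a later drug with response rate r. Then p_B = 0.18 + 0.82 × f × r.
- f = 0.05, r = 0.10: p_B = 0.184; odds ratio = (0.184/0.816)/(0.18/0.82) = 1.03.
- f = 0.20, r = 0.30: p_B = 0.229; odds ratio = (0.229/0.771)/(0.18/0.82) = 1.35.
- If the extra switching is in arm A instead, the odds ratios invert: 1/1.03 = 0.97 and 1/1.35 = 0.74.
- If only responses before new therapy count, both arms stay at 18% and the odds ratio is 1.00.

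**4. Illustration for PFS (simulation, assumed values).** Assume a true hazard ratio of 1.00 and a median of 2 months in both arms (the control assumption in SAP 5.1). A fraction of patients event-free at 2 months switch, unrelated to prognosis, to a drug that multiplies the hazard by 0.5 to 0.75.

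| Switching, B vs A | HR, SAP rule | HR, censored at new therapy |
|---|---|---|
| 10–30% vs 0% | 0.89–0.98 | about 1.00 |
| 20% vs 20% | about 0.99–1.00 | about 0.99–1.00 |
| 10% vs 30% | 1.03–1.07 | about 1.00 |

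Censoring looks clean here only because switching was made independent of prognosis.

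**5. Direction.** Protocol 8.11 (GRASPA toxicity) and 8.4 (supply failure) are exits open to arm B alone. Against that, under protocol 8.5.3 an arm B patient who stops cytarabine for toxicity continues GRASPA, while an arm A patient then has no study drug. Protocol 8.5.4 speaks of discontinuing GRASPA and 8.11 of stopping study treatment. These must be reconciled before anyone can say what ends after GRASPA toxicity.

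**The case against.** The quoted denominator sentence is not itself wrong, and exposure is narrow. After relapse or resistant disease patients are followed for survival (protocol 8.11), so later-drug responses arise mainly in those who stop earlier, and the assumed control median PFS is only 2 months. Both points stand. They limit the size without supplying the missing rule.

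A reader might infer more than the documents support:

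- **That the later-therapy data are never used.** SAP 5.2.8 puts everything recorded on the CRF into data listings, and SAP 1 leaves output specifications to a separate document. What is missing is an endpoint rule and a named by-arm table.
- **That later therapy is pooled with concomitant medication**, because SAP 5.8.4 says "All other medications reported will be considered as concomitant". Subsequent AML therapy has its own row in the schedule, and nothing says it enters that dataset. Pooling is possible but not shown.
- **That the PFS rule is an error.** Following all randomised patients through later therapy is a legitimate ITT choice. The per-protocol set may also drop some patients for disallowed treatments (SAP 4.2; protocol 10.2), though it sets no rule for therapy after study treatment ends.
- **That the bias favours GRASPA.** Step 5 above shows asymmetry both ways.
- **That the OS reading against 0.80 is undermined.** OS regardless of later therapy is the right primary analysis. OS was simulated with no true effect, a control median of 6.4 months, switching at month 3 and unequal switch rates (30% vs 15% or 40% vs 20%, in either direction). With assumed hazard multipliers of 0.5 to 0.6, the hazard ratio ran from about 0.90 to 1.10 and never reached 0.80. Even with all 123 patients dead, SE(log HR) is about √(1/82 + 1/41) = 0.19, so the move to 0.90 is 0.11/0.19, about 0.6 of one standard error.

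**Conclusion.** The point holds as an omission in the response definition. As written, the plan credits a remission on a later drug to the randomised arm, at 1.2 points per patient in arm B and 2.4 in arm A. For PFS and RFS the rule is defensible, but no supporting analysis shows how far later therapy affects the result. The OS analysis should not change; it lacks only a by-arm description of later therapy to read beside it.

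The odds ratios of 1.03–1.35 (inverted, 0.97–0.74) and PFS hazard ratios of 0.89–1.07 rest on assumed switch rates, later-drug activity and an 18% base rate. They show that the effect could be visible in either direction. They do not estimate it. The matter should be settled before database lock but does not threaten the primary analysis.

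**What to change.** - **SAP 5.6.2.1:** count CR, CRi and PR only from assessments on or before the start of the first subsequent AML therapy. State that RFS takes its responders from the same rule; otherwise a patient could enter RFS after the date at which the sensitivity analysis censors.
- **SAP 5.6.2.2 and 5.6.2.3:** keep the ITT rule. Add one sensitivity analysis that censors at the start of new therapy and one that counts it as an event. Note that this censoring may be informative.
- **SAP 5.6:** leave ITT OS unchanged.
- **SAP 8.1:** add a by-arm table of subsequent AML therapy (number of patients, agent, time from randomisation) to read beside the OS hazard ratio.
- **SAP 5.8.4:** leave the concomitant-medication window as it is, since AEs are collected for 4 months after the last dose (protocol 11.1.2.2). Tabulate antineoplastics started after the end of study treatment separately.
- **Protocol 8.5.4 and 8.11:** reconcile what stops after GRASPA toxicity.

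The cost is SAP wording, one or two tables and two sensitivity analyses. A few late responses may be lost from the response rate. Agent and start date must first be confirmed as recorded on the eCRF, because protocol Table 6 and the text of 8.10 differ on when later therapy is asked about.

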15.3.1 Primary endpoint analysis

The primary endpoint will be analyzed based on the ITT population. Efficacy data will also be analyzed on the Per-Protocol population to assess sensitivity of results to protocol compliance.

The primary objective of the trial is to estimate whether GRASPA plus low-dose cytarabine is more promising than low-dose cytarabine alone with respect to OS in subjects 65-85 years old with newly diagnosed AML unfit for intensive chemotherapy. OS will be calculated from date of randomization to date of death (or censoring).

OS will be summarized using Kaplan-Meier methods. The analysis of OS, will be performed using a stratified log-rank test (stratification factor PS (0, 1 vs 2) to compare treatment groups).

Hypothesis testing will be based on the following relations:

H0 : $\theta = -\log(\lambda) = 0$ and the alternative hypothesis will be H1 : $\theta = \theta 1 > 0$ where λ is the hazard ratio (HR) between the GRASPA plus low-dose cytarabine and the low-dose cytarabine alone groups. In our case (assumption for the median survival times of 2 months and 3.5 months for low-dose cytarabine alone and GRASPA plus low-dose cytarabine respectively) this will mean that H1 : $\theta = -\log(0.5714) = 0.5597$.

A secondary analysis will be performed using Cox's proportional hazards regression model, allowing for the effect of treatment and prognostic factors (ECOG, age and cytogenetic group). For the main criterion of efficacy the significance level will be 0.05 using a two-sided test.

The primary analysis for OS will take place once all patients have completed 12 months in the study. It should be noted however that the study is not powered explicitly for OS and statistical significance in favor of GRASPA plus low-dose cytarabine is not anticipated. A decision as to whether GRASPA appears to be a promising drug in this indication will be based on the numerical values for the hazard ratio for OS. A hazard ratio of ≤ 0.80 will indicate a 20% numerical reduction in the death rate on average over time in the GRASPA group compared to control.

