15.3.3 Secondary endpoint analysis

Efficacy endpoints

All efficacy secondary endpoints will be analyzed in the ITT and PP populations.

Progression-free survival (PFS) will be analyzed as a secondary criterion of efficacy. PFS will be defined as the time from date of randomization and resistant disease or relapse or death from any cause. Any patient not known to have died at the time of analysis will be censored based on the last recorded date on which the patient was known to be alive (i.e. their status must be known at the censored date and should not be lost to follow up or unknown). PFS will be analyzed at the time of final analysis using a stratified log-rank test (stratification factor, PS). A Cox model will also be used to test the effect of treatment and will include terms for prognostic factors (PS, age and cytogenetic group).

The analysis of objective response rate (i.e. CR or PR) will be performed using logistic regression including treatment factor and PS. Secondary analysis will be performed where the logistic regression model will allow for the effect of treatment, and will also include prognostic factors as for OS and PFS. Percentage of patients with CR, CRi, CRp and PR will be calculated and associated exact 95% CIs will be presented by treatment group. Median duration of response from onset of response (RFS) will be calculated and summarized by treatment group for the subset of responders.

Absolute and relative change from baseline EORTC quality of life (QoL) questionnaire scores will be described in each treatment group. EORTC QoL questionnaire scores will be compared across time in each treatment group using a mixed model for repeated data.

Time until QoL deterioration will be defined as a decrease in QoL score from baseline without any return to a better state during the study. A threshold of 10% decrease in QoL score will be primarily used. Other thresholds may be used as exploratory analyses. Death will also be considered as a QoL deterioration. Time to QoL deterioration will be summarized using Kaplan-Meier methods and will be compared between treatment groups using a stratified log-rank test (stratification factor, PS).

Percentage of patients who need transfusions (red blood cells and/or platelets), mean number of transfusions by patient and mean number of hospitalizations (more than over 24 hours) required during the study will be described with their corresponding 95% CI in each treatment group.

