5.2.4. Adjustments for Covariates

No formal statistical analysis that adjusts for possible covariate effects is planned.

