5.6.1. Sensitivity Analyses for the Primary Endpoint

The analyses described in Section 4.6 will also be repeated on the PP population and separately for patients recruited before and after the protocol amendment to assess sensitivity of results to protocol compliance and amendment.

A further sensitivity analysis will be undertaken based on a stratified Cox Model, stratified for PS (0 or 1 versus 2), and including age (< 70 / ≥ 70) and Karyotype (Intermediate risk / High risk) as covariates.

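### The SAP omits, without declaring it, the protocol's supporting response model adjusted for age and cytogenetic group, and SAP 5.2.4 contradicts the adjusted models the SAP does keep

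*SAP*

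**What the plan says.** **Protocol.** Section 15.3.3 sets out two response analyses. The main one: "The analysis of objective response rate (i.e. CR or PR) will be performed using logistic regression including treatment factor and PS". The secondary one is a logistic model that "will allow for the effect of treatment, and will also include prognostic factors as for OS and PFS". Sections 15.3.1 (OS) and 15.3.3 (PFS) name the same three factors: PS (ECOG), age and cytogenetic group. The secondary model is worded as an analysis that will be done, not as an option.

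**SAP.** Section 5.6.2.1 has response "analyzed based on a logistic regression model with both treatment and PS included in the model", and then: "The treatment effect will be summarized with an adjusted Odds Ratio (OR) and 95% confidence interval". No second response model appears. Section 5.2.4 states: "No formal statistical analysis that adjusts for possible covariate effects is planned". Yet section 5.6.1 keeps an adjusted Cox model for OS, stratified for PS "and including age (< 70 / ≥ 70) and Karyotype (Intermediate risk / High risk) as covariates", and sections 5.6.2.2 and 5.6.2.3 keep Cox models with PS, age and karyotypic group for PFS and RFS.

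**Declared changes.** SAP 2 undertakes to outline differences from the protocol. SAP 6 lists the PFS definition, the move from PFS to OS and the interim analysis that was not done. It does not mention the response model.

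**The concern.** Activity is to be judged on the totality of evidence across endpoints (SAP 1), and response heads the list of secondary efficacy endpoints (SAP 3.5.1). Randomisation is stratified on PS only (protocol 7.4, SAP 3.2). The protocol's introduction (3.1) names older age and unfavourable karyotype as adverse prognostic factors. With 41 and 82 patients, the arms can differ by chance in either factor. The protocol provided a supporting model to show whether such a difference matters for response, and under the SAP a reader of the study report would not have it.

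The second problem is internal. An analyst who follows 5.2.4 cannot also follow 5.6.1, 5.6.2.1, 5.6.2.2 and 5.6.2.3. The sentence could be cited either to justify the missing response model or to drop the adjusted models that remain.

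**Working it through.** The discrepancy itself rests on the text. Neither document gives a figure for it, so there is nothing to reproduce.

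**1. Documents side by side**

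| Endpoint | Protocol adjusted model | SAP text | SAP 8.1 output list |
|---|---|---|---|
| OS | Cox: ECOG, age, cytogenetic group | kept (5.6.1) | Cox tables with prognostic factors |
| PFS | Cox: PS, age, cytogenetic group | kept (5.6.2.2) | Cox tables with prognostic factors |
| Response, main | logistic: treatment, PS | kept (5.6.2.1) | summary table |
| Response, secondary | logistic: treatment plus factors as for OS and PFS | absent | no model table; subgroup table only |

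Of the protocol's three adjusted models for OS, PFS and response, only the response one is missing. The output list only corroborates this: RFS has a Cox model in the SAP text but no Cox table in the list.

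**2. Size of chance imbalance**

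Inputs: arms of 41 and 82 (SAP 5.1) and a high-risk share p, which is assumed. The standard deviation of the between-arm difference is sqrt(p(1 − p)(1/41 + 1/82)).

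- p = 0.30: sqrt(0.21 × 0.03659) = 0.088
- p = 0.40: 0.094
- p = 0.50: 0.096

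So it is about 9 percentage points across this range.

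**3. What one such imbalance does to the PS-only odds ratio**

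Assume no treatment effect, 18% response, 40% high risk, and an odds ratio of 0.5 to 0.15 for response in high-risk patients. An imbalance favouring GRASPA then gives an apparent odds ratio of 1.06 to 1.15 at 1 SD and 1.13 to 1.33 at 2 SD. This is what the supporting model would reveal in a given trial. Over repeated randomisations it averages out.

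**4. Average behaviour of the two models**

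This comes from simulated trials of 41 and 82 patients, about 3,000 per setting, 30% high risk, fitted with and without karyotype.

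- *No treatment effect:* the median odds ratio is about 1.00 from both models. With a karyotype odds ratio of 6, type I error is 4.1% without karyotype and 4.4% with it; at 2 it is 4.6% for both.
- *18% v 40%:* with a karyotype odds ratio of 6, power goes from 70% to 74% in one run and from 71% to 75% in another. At 2 it goes from 71% to 72% and from 70.5% to 71.5%.
- *Range:* over these settings and 18% v 30%, the runs gave gains from 0.3 to about 4 points.
- *Agreement:* with a true effect, the two models disagreed on two-sided 5% significance in 4% to 9% of trials; with none, in 1% to 2%.

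**5. Shift in the odds ratio**

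At 18% v 40% with a karyotype odds ratio of 6, one run's median odds ratio moves from 3.07 to 3.38 when karyotype is added. The marginal odds ratio is (0.40/0.60)/(0.18/0.82) = 3.04. The odds ratio conditional on karyotype that yields the same two response rates is 3.35. Each median lies close to its own target, so the shift is mostly non-collapsibility.

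**The case against.** Several objections have force.

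- **The main analysis is unchanged.** The protocol's main response model is also treatment plus PS. A reader might infer that the SAP has made the response odds ratio ignore age and cytogenetic risk. The documents do not support that: the main odds ratio leaves both out under either document, and only the supporting analysis has gone.
- **There is no average bias.** A reader might take the move from 3.07 to 3.38 as bias from leaving out karyotype. It is not: the two models estimate different quantities, and with no effect both centre on 1.
- **Age and karyotype are not absent from the response analysis.** SAP 5.2.6 gives response effects with 95% confidence intervals by age and karyotype subgroup. This partly mitigates the loss, but subgroup estimates are not one overall effect adjusted for both factors.
- **SAP 5.2.4 might be read as the declaration.** It is not presented as a change from the protocol, and the SAP's own adjusted models contradict it.
- **The promising-drug decision rests on the OS hazard ratio** (SAP 5.1), and adjusted OS and PFS models remain. That limits the weight of this point. Response still counts under SAP 1.
- **The numerical inputs are soft.** The 18% is a complete remission rate from a study cited in protocol 3.1, not a design rate for CR, CRi or PR. The experimental-arm rates, high-risk share and karyotype effects are assumptions.

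**Conclusion.** The point holds as an undeclared departure from the protocol and an internal contradiction in the SAP. A pre-planned supporting model for response is missing, SAP 6 is silent on it, and SAP 5.2.4 cannot stand beside SAP 5.6.

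The consequence is modest. The check that is lost guards against an imbalance whose SD is about 9 points for karyotype, and the forgone power is about 0 to 4 points. Both figures depend on the assumed high-risk share, and the second also on assumed response rates and karyotype effects. The textual finding depends on none of these. Nothing here shows that the trial's conclusion would change. The case for acting is that the model was already planned, uses baseline data already collected and costs almost nothing.

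**What to change.** 1. In SAP 5.6.2.1, restore the secondary logistic model with treatment, PS, age and karyotype; the age and karyotype categories in SAP 5.6.1 can be reused. State that the outcome is the SAP's response definition (CR, CRi or PR), because protocol 15.3.3 describes objective response as CR or PR.
2. Report its odds ratio and 95% confidence interval beside those of the main model, and add a matching table to SAP 8.1.
3. Correct SAP 5.2.4 to point to the adjusted models in SAP 5.6.
4. If the sponsor prefers to leave the model out, declare and justify this in SAP 6. That removes the inconsistency but not the loss of the check.

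A penalised fit may be used if responders are sparse. At 18%, the control arm would have 41 × 0.18 = 7.4 responders, possibly more once CRi and PR are counted. This is optional and not part of the protocol's plan.

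The cost is one extra model, one table and a few lines of SAP text. No new data are needed.
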